## **Cognitive Assessment:**

Each participant will undergo a neuropsychological evaluation before (T0) and immediately after the end of the robotic training (T1). The evaluation will be conducted by a neuropsychologist to ensure that cognitive assessments and interpretations of results remain unbiased and objective. We considered to use different neuropsychological tests to investigate specific cognitive domains to obtain a more complete neuropsychological profile.

### ***Parkinson population***

For this target, the assessment will include a global cognitive evaluation using: Addenbrooke's Cognitive Examination Revised (ACE-R) was designed as a valid screening instrument for cognitive profile. It assesses different cognitive domains: attention and concentration, executive functions, memory, language, visuo-spatial skills, conceptual reasoning and orientation; Wisconsin Card Sorting Test (WCST) assesses executive functioning, in particular, cognitive flexibility in problem solving, inability to abstraction and perseveration; Corsi Block-Tapping Test evaluates span of visual-spatial memory; Trail Making Test (TMT) assesses selective attention and cognitive flexibility; Rey-Osterrieth Complex Figure Test assesses visual-constructive and visual-spatial memory capabilities; Symbol Digit Modalities Test (SDMT) examines sustained attention and working memory; Parkinson's disease questionnaire-39 (PDQ-39) is a 39-item self-report questionnaire, which assesses Parkinson's disease-specific health related quality in 8 dimensions: Activities of Daily Living, Attention, Working Memory, Cognition, Communication, Depression, Functional Mobility, Social Relationships and support.

### ***Multiple Sclerosis population***

For this target, the assessment will include a global cognitive evaluation using: Brief Repeatable Neuropsychological Test (BRNT) that includes several sub-tests to assess memory, attention, and executive functions, specifically designed for multiple sclerosis; The MSQOL-54 is a multidimensional health-related quality of life measure that combines both generic and MS-specific items into a single instrument.

### ***Stroke population***

For this target, the assessment will include a global cognitive evaluation using: Repeatable Battery for the Assessment of Neuropsychological Status (RBANS) is a brief, individually administered test that helps determine the neuropsychological status. It includes different cognitive tasks: attention and concentration, executive functions, memory, language, visuo-spatial skills, conceptual reasoning

and orientation tasks; Tower of London (TOL) assesses the ability to plan and solve complex problems; Rey-Osterrieth Complex Figure Test assesses visual-constructive and visual-spatial memory capabilities; Stroke Specific Quality of Life Scale (SSQOL) assesses several domains, including physical function, cognition, emotions, communication, and social life.

At the end of the rehabilitative training we used a scale for evaluate the main dimensions of usability by using System Usability Scale robotic (SUS-r) and Goal Attainment Scaling (GAS).

### **Motor Assessment:**

Each participant will undergo by a motor evaluation before (T0) and immediately after the end of the robotic training (T1). The evaluation will be conducted by physiotherapist. It includes: Fugl-Meyer Assessment – Upper Limb (FMA-UL) comprises of five domains: motor functioning (in the upper and lower extremities), sensory functioning, balance, joint range of motion and joint pain. It includes items assessing movement, coordination, and reflex action of the shoulder, elbow, forearm, wrist, hand; Motricity Index (MI) for the upper limb assess upper extremity function and functional mobility; Disability of the Arm, Shoulder and Hand (DASH) assesses musculoskeletal disorders of the shoulder, hand and arm; Nine Hole Peg Test (9HPT) and Box and Block Test (BBT) measure unilateral gross manual dexterity; Test del monofilamento di Semmes Wilson assesses whether alterations in skin sensitivity are present.

### **Inclusion criteria**

- Age 18-75 years;
- FMA-UL 0-31: eligible for exoskeletons and robotic devices with high support. (Armeo Power, Amadeo, Motore)
- FMA-UL 32-47: eligible for end-effectors with medium support. (Armeo Spring, Hand Tutor, Diego)
- FMA-UL 48-52: eligible for sensor-based with low support. (Pablo, Diego, Armeo Senso)
- MoCA: ≤20

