### **Secondary Objectives:**

- Analyze the correlation between specific cognitive deficits and motor recovery in patients undergoing robotic rehabilitation training
- Investigate the role of motor rehabilitation integrated with cognitive tasks in improving cognitive and motor functions.
- Analyse the impact of robotic rehabilitation on mood and psychological well-being.
- Compare the effectiveness of robotic rehabilitation training among different subgroups of neurological patients (Stroke- Multiple sclerosis- Parkinson's disease).

- Explore the influence of individual patient characteristics (age, severity of cognitive impairment, disease stage) on cognitive rehabilitation outcomes.

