## **METHODS AND PROCEDURES OF THE STUDY**

The current study will follow the following timeline:

*T0. Baseline:* Initially, patients will be recruited and randomly assigned to one of two groups using block randomization. This method divides participants into small blocks and assigns an equal number of patients to each group within each block. For example, in a block of four participants, two will be assigned to group A and two to group B. This process is repeated for each block, ensuring that both groups have a balanced number of participants throughout the study.

SBRR will receive motor and cognitive rehabilitation assisted by robotic and sensor-based devices through Motore, Armeo Senso, Hand Tutor, Armeo Power, Armeo Spring, Pablo, Amadeo, Diego. SCT will receive conventional motor rehabilitation treatment.

Subsequently, patients will undergo a neurological examination, comprehensive neuropsychological assessment, and motor evaluation. These assessments will be conducted in a blinded modality, with evaluators distinct from recruiters and therapists. Importantly, the evaluators will not be aware of the group assignment of the patients.

Following these assessments, both groups will engage in their respective rehabilitation programs. Each session will perform for 60 minutes 2-3 times a week for a total of 25 sessions.

*T1. Post-intervention assessment:* At the end of the rehabilitation program, a comprehensive neuropsychological and motor assessment will be conducted again.

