## ***STATISTIC ANALYSIS***

A descriptive analysis of the sample will be performed for socio-demographic and clinical variables. The Shapiro-Wilk test will be applied to assess the distribution type of the variables. Continuous variables will then be expressed as mean $\pm$ SD, while categorical variables will be presented as frequencies and percentages. The parameters evaluated will include the motor and cognitive test scores.

- For intra-group analysis, a paired T-test or Wilcoxon signed-rank test will be applied, depending on the data type, to compare the scores between the two time points. Additionally, the Pearson correlation coefficient will be calculated for parametric data, or Spearman's correlation for non-parametric data, to examine whether a relationship exists between demographic and clinical variables. Multiple regression analyses will be performed on the cognitive scores treated as dependent variables. Initially, we will focus on the influence of motor scores as predictors. A backward elimination stepwise procedure will be applied to select the best predictive variables according to the Akaike Information Criterion (AIC).
- For inter-group analysis, an unpaired T-test or Mann-Whitney U test will be applied to compare the groups at T0 and T1. Additionally, ANCOVA will be used with T1 cognitive scores as the dependent variable, group (SBRR vs. SCT) as the independent variable, and T0 cognitive scores and age as covariates, to determine whether the rehabilitation method (SBRR vs. SCT) has a true effect on cognitive improvement independent of baseline scores and age.

All analyses will be conducted using the open-source software package R4.2.2. A 95% confidence level will be established, with an alpha error of 5%. Statistical significance will be set at  $p < 0.05$ .

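### SBRR support level is set by baseline FMA-UL, yet FMA-UL enters no stated between-group model, so the secondary comparison among stroke, MS and Parkinson's disease may mix disease with support level and motor severity

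*Protocol*

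**What the plan says.** - **Treatment by band (Protocol, Inclusion criteria).** Three FMA-UL bands each carry a support level and a device list: "FMA-UL 0-31: eligible for exoskeletons and robotic devices with high support", then "FMA-UL 32-47: eligible for end-effectors with medium support. (Armeo Spring, Hand Tutor, Diego", then "FMA-UL 48-52: eligible for sensor-based with low support. (Pablo, Diego, Armeo Senso". Each band lists three devices, and Diego appears in two bands.
- **Control and allocation (Protocol, Methods and Procedures).** "SCT will receive conventional motor rehabilitation treatment", with no division by band. Patients are "randomly assigned to one of two groups using block randomization", in a 1:1 ratio. No stratum for FMA-UL or for disease is stated.
- **Disease comparison (Protocol, Secondary Objectives).** One objective is to "Compare the effectiveness of robotic rehabilitation training among different subgroups of neurological patients", namely stroke, multiple sclerosis and Parkinson's disease. A further objective names age, cognitive severity and disease stage as characteristics to explore. Motor severity is not named.
- **Models (Protocol, Statistic Analysis).** The between-group tests are an unadjusted t-test or Mann-Whitney test and an ANCOVA with "T0 cognitive scores and age as covariates". Motor scores appear only as candidate predictors of cognitive scores in a regression listed under the intra-group analysis, subject to backward elimination by AIC. No model is given for the disease comparison.
- **Data (Protocol, Motor Assessment).** FMA-UL is measured at T0 and T1 in every participant.

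**The concern.** The disease objective treats robotic rehabilitation as one treatment, but the inclusion criteria make it three support levels chosen by baseline motor status. Disease is not randomised and recruitment is purposive, so nothing in the design makes the band mix alike in the three diseases.

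If the mixes differ and the benefit over control depends on the band, the trial could report that robotic rehabilitation works better in one disease when only the distribution over bands differs. The protocol itself puts motor scores first among the candidate predictors of cognitive scores, so it cannot take motor status to be irrelevant.

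**Working it through.** **The plan's own figure.** The protocol gives no figure on this point. Its sample size of 52 per group (paired t-test, d = 0.4, two-sided 0.05, power 0.80) reproduces: exact power at n = 52 is 0.808. That calculation plays no part here. I only borrow 52 as an illustrative number per arm per disease.

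**Where FMA-UL appears.**

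| Element | Carries FMA-UL or band? |
|---|---|
| SBRR support level | Yes, sets it |
| SCT treatment | No |
| Randomisation strata | None stated |
| Unadjusted between-group tests | No |
| ANCOVA covariates | No |
| Characteristics named for exploration | No |
| Intra-group regression | As a candidate that may be dropped |

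**Size of a spurious disease difference.** Assume the SBRR-SCT effect in each band is the same in every disease, so that there is no true disease difference. For diseases A and B:

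spurious difference = sum over bands of (share in A − share in B) × band effect.

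The protocol gives neither the shares nor the effects, so all of these inputs are assumptions. The last column is the chance of a significant group-by-disease result at a nominal 5%, with SD 1, 52 per arm per disease and a normal approximation: SE = sqrt(4/52) = 0.277.

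| Band effects, SD (high/medium/low support) | Band mixes, A vs B (%) | Mean effects, A and B | Difference | Rejection |
|---|---|---|---|---|
| 0.4/0.4/0.4 | any | 0.40, 0.40 | 0 | 5.0% |
| 0.2/0.4/0.6 | equal | 0.40, 0.40 | 0 | 5.0% |
| 0.3/0.4/0.5 | 50/30/20 vs 20/30/50 | 0.37, 0.43 | 0.06 | 5.5% |
| 0.3/0.4/0.5 | 70/20/10 vs 10/20/70 | 0.34, 0.46 | 0.12 | 7.2% |
| 0.2/0.4/0.6 | 50/30/20 vs 20/30/50 | 0.34, 0.46 | 0.12 | 7.2% |
| 0.6/0.4/0.2 | 60/30/10 vs 10/30/60 | 0.50, 0.30 | 0.20 | 11.1% |
| 0.2/0.4/0.6 | 70/20/10 vs 10/20/70 | 0.28, 0.52 | 0.24 | 13.9% |

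For the 0.20 row: 0.6×0.6 + 0.3×0.4 + 0.1×0.2 = 0.50, and 0.1×0.6 + 0.3×0.4 + 0.6×0.2 = 0.30. Both conditions are needed: a flat effect or equal mixes gives zero.

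**Which adjustment removes it.** I took the 0.20 SD case with 1:1 arms in every cell and fitted three models by weighted least squares to the cell means:

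| Model | Group-by-disease difference | SE |
|---|---|---|
| group × disease | 0.20 | 0.277 |
| group × disease + band | 0.20 | 0.277 |
| group × disease + group × band | 0 | 0.346 |

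The band main effect changes nothing because band is balanced between arms within each disease. The distortion lies in how the treatment effect varies with band.

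The larger SE can be checked by hand. Per-arm counts are 31.2, 15.6 and 5.2 in A, and the reverse in B. The variance of the disease difference within a band is 2/n_A + 2/n_B, which gives 0.4487, 0.2564 and 0.4487. The precisions are 2.23, 3.90 and 2.23, which sum to 8.36. So SE = sqrt(1/8.36) = 0.346, about 25% wider (0.346/0.277 = 1.25).

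**The case against.** - **The disease comparison has no stated model.** Its covariates may sit in a statistical analysis plan that is not shown. This stands, and the absence of a model is not the point here. The point is that the covariates and the explored characteristics which the protocol does name leave out the variable that sets the support level.
- **A reader might infer that the disease comparison is confounded as a matter of fact.** The documents do not support that. They give no band distribution by disease and no evidence that the effect differs by band.
- **A reader might infer that SBRR versus SCT is biased.** It is not. FMA-UL is a baseline trait and is balanced in expectation by randomisation, so the contrast averages over the band mix. The planned T0 comparison of the groups would also show a chance imbalance in motor scores. Adjustment there is about precision and protection against such imbalance.
- **A reader might infer that band fixes the device.** It fixes the support level only: each band lists three devices, and Diego is in two.
- **Comparing severity-matched robotic treatment as delivered is a legitimate question.** True, since the rationale presents tailored assistance as a strength. But the answer then describes a disease with its band mix, and the report must say so.
- **The disease comparison is limited anyway by different primary instruments** (ACE-R, Rao's battery, RBANS). This also stands; it is a separate limitation that adjusting for band does not cure.

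**Conclusion.** The point holds in a limited form. Support level in SBRR follows baseline FMA-UL, and no stated between-group model, stratum or named effect modifier carries FMA-UL. The secondary disease comparison may therefore mix disease with support level and motor severity.

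Over the assumed inputs the spurious difference is 0 to 0.24 SD, with rejection between 5% and 13.9%. The upper end needs both strongly different band mixes and effects that vary threefold across bands. The 0.20 SD case is an illustration and should not be set against d = 0.4, which belongs to a paired, within-group test and is on a different scale.

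No analysis can separate support level from motor severity within SBRR, because one is defined by the other. Adjustment can only compare the diseases at equal band.

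**What to change.** 1. **SBRR versus SCT:** add T0 FMA-UL as a covariate in the ANCOVA.
2. **Disease comparison:** state that it compares SBRR-SCT differences between diseases, in a model with group-by-disease and group-by-FMA-UL (or group-by-band) terms. Define the band in the same way for SCT patients, from their T0 score.
3. **Reporting:** tabulate band by arm and disease, and device by disease in SBRR. Limit conclusions to the bands that the diseases share.
4. **Limitation:** state that support level cannot be separated from motor severity within SBRR.

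This is analysis and reporting wording only. T0 FMA-UL is already measured in every participant, and no device or eligibility rule changes. With three bands, the main effect uses two degrees of freedom and the group-by-band term two more; continuous FMA-UL uses one for each. The interval for the disease comparison widens, by about 25% in the 60/30/10 versus 10/30/60 illustration, and the conclusion must be more guarded where a disease occupies few bands.

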### **Exclusion criteria**

- Severe cognitive disorders
- Behavioral disorders
- Sensory disorders

## ***DURATION OF THE STUDY***

The study duration will be 60 months.

## ***STATISTIC ANALYSIS***

A descriptive analysis of the sample will be performed for socio-demographic and clinical variables. The Shapiro-Wilk test will be applied to assess the distribution type of the variables. Continuous variables will then be expressed as mean $\pm$ SD, while categorical variables will be presented as frequencies and percentages. The parameters evaluated will include the motor and cognitive test scores.

- For intra-group analysis, a paired T-test or Wilcoxon signed-rank test will be applied, depending on the data type, to compare the scores between the two time points. Additionally, the Pearson correlation coefficient will be calculated for parametric data, or Spearman's correlation for non-parametric data, to examine whether a relationship exists between demographic and clinical variables. Multiple regression analyses will be performed on the cognitive scores treated as dependent variables. Initially, we will focus on the influence of motor scores as predictors. A backward elimination stepwise procedure will be applied to select the best predictive variables according to the Akaike Information Criterion (AIC).
- For inter-group analysis, an unpaired T-test or Mann-Whitney U test will be applied to compare the groups at T0 and T1. Additionally, ANCOVA will be used with T1 cognitive scores as the dependent variable, group (SBRR vs. SCT) as the independent variable, and T0 cognitive scores and age as covariates, to determine whether the rehabilitation method (SBRR vs. SCT) has a true effect on cognitive improvement independent of baseline scores and age.

All analyses will be conducted using the open-source software package R4.2.2. A 95% confidence level will be established, with an alpha error of 5%. Statistical significance will be set at  $p < 0.05$ .

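### P-values and intervals read from the backward-AIC regression of cognitive on motor scores will not have the 5% and 95% properties that the protocol sets for all analyses

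*Protocol*

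**What the plan says.** Within the intra-group bullet of STATISTIC ANALYSIS, the Protocol says: "Multiple regression analyses will be performed on the cognitive scores treated as dependent variables". On the candidate predictors: "Initially, we will focus on the influence of motor scores as predictors". On how the model is reduced: "A backward elimination stepwise procedure will be applied to select the best predictive variables according to the Akaike Information Criterion (AIC").

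The section closes with one rule for everything, naming no exception: "A 95% confidence level will be established, with an alpha error of 5" per cent, and significance at p < 0.05.

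Motor Assessment lists six measures: FMA-UL, Motricity Index, DASH, Nine Hole Peg Test, Box and Block Test and a monofilament test. The last measures skin sensitivity, so one may count five or six motor scores. The number that enters the regression is not given. The relation between cognitive deficits and motor recovery is the first item under Secondary Objectives.

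**The concern.** AIC does not screen at 5%. It keeps a term whenever dropping it would raise the likelihood-ratio statistic by more than 2, which for one coefficient corresponds to a p-value of about 0.157. The survivors are then tested on the data that selected them, so their ordinary t-tests and confidence intervals ignore the search.

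The candidates also overlap, since most of them measure the same upper limb. With correlated predictors, elimination can keep whichever one happens to fit best, and the distortion grows.

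At stake is the secondary finding on which motor scores go with which cognitive scores. A reader would take a reported predictor with p < 0.05 as a 5% claim, and its interval as a 95% interval. Neither would be right.

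**Working it through.** **Inputs from the Protocol.** Selection rule, candidate type and alpha come from STATISTIC ANALYSIS. The count of k = 6 measures, or 5 without the monofilament test, comes from Motor Assessment. The n of 52 per group comes from Sample Size. That 52 reproduces: a paired t-test with d = 0.4 and two-sided 0.05 has power 0.808 at n = 52 and 0.7999 at n = 51. The Protocol states no error rate for the regression, so there is no figure of its own to reproduce on this point.

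**Assumptions.** That five or six scores enter; pairwise correlation ρ from 0 to 0.7; no motor score related to the cognitive score (the null); and ordinary t-tests at p < 0.05 on the selected model, as the closing rule implies.

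**Analytic checks.**
- Per-term retention under the null: P(χ² with 1 df > 2) = 0.157.
- At least one of six independent null terms retained: 1 − (1 − 0.157)^6 ≈ 0.64.
- At least one of six independent 5% tests significant with no selection: 1 − 0.95^6 = 0.265; for five, 1 − 0.95^5 = 0.226.
- Share of retained independent null terms with p < 0.05: about 0.05 / 0.157 = 0.32, so their nominal 95% intervals cover zero about 68% of the time rather than 95%.

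**Simulation.** Null data, backward elimination by AIC, n = 52, k = 6, 4,000 data sets per setting:

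| ρ | At least one noise term kept | At least one kept with p < 0.05 | Full model, any coefficient p < 0.05 | Full model, overall F-test p < 0.05 |
|---|---|---|---|---|
| 0 | 68.1% | 28.9% | 24.4% | 5.3% |
| 0.3 | 68.5% | 34.3% | 23.6% | 5.0% |
| 0.5 | 69.8% | 39.4% | 24.8% | 4.9% |
| 0.7 | 71.7% | 43.6% | 23.2% | 5.3% |

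With k = 5 the third column runs from about 26% (ρ = 0) to 37.1% (ρ = 0.7); at ρ = 0.7 the unselected model gives 21.4% and its F-test 5.0%.

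**What selection adds.** For k = 6: 28.9 − 24.4 = 4.5 points at ρ = 0, and 43.6 − 23.2 = 20.4 points at ρ = 0.7. For k = 5 at ρ = 0.7: 37.1 − 21.4 = 15.7 points.

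**Interval coverage.** Among retained null terms, nominal 95% intervals cover zero about 56 to 67% of the time, with the lower figure at the higher correlation.

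**Repeat run.** With 6,000 data sets per setting, the rate was 25.4 to 35.5% for k = 5 and 30.2 to 43.5% for k = 6. The unselected model gave 20.0 to 25.4%, and coverage was 55 to 68%. These agree with the figures above to within about two points. When full-model coefficients were read only after a significant overall F-test, the false-positive rate was 4.4 to 4.8%.

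**Sensitivity.** Sample size matters little: for k = 6 and ρ from 0 to 0.7, n = 126 gives 28.8 to 42.9%. The number of candidates matters more: at n = 52 over the same ρ, k = 4 gives 20 to 29% and k = 3 gives 15 to 21%.

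**The case against.** Several points on the other side stand.

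- **Much of the rate is multiplicity.** A reader might infer that AIC selection alone turns 5% into some 30 to 45%. It does not: testing six coefficients of a prespecified model without adjustment already gives 23 to 25%. Only the difference belongs to selection.
- **Key inputs are not in the document.** The number of scores and their correlation are assumed, and with three or four candidates the rates are lower.
- **P-values on the selected model are inferred.** The regression sentences speak only of choosing predictors. The inference rule comes from the closing sentence. Since that sentence covers all analyses, the inference is the natural reading, but it remains an inference.
- **The null may be false.** A reader might infer that the trial will report noise. The figures apply when no motor score relates to the cognitive score, and the rationale argues that cognition and motor function are linked. The rates describe a loss of error control; they do not predict the result.
- **Reach.** One might infer that the intended guidelines would rest on these predictors. The section on expected outcomes ties the guidelines to building cognitive tasks into robotic rehabilitation, which is a different question.
- **What an SAP may add.** A missing exploratory label or validation step could be left to an SAP and is not the complaint here.

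What does not fall away is that the Protocol itself fixes both the selection rule and a 5% / 95% rule without exception, and the two are incompatible.

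**Conclusion.** The point holds, as a flaw in a secondary analysis. Applied as written, the 5% and 95% levels are not met by models chosen through backward AIC on the same data. Under the null, with five or six candidates, n = 52 and correlation 0 to 0.7, a spurious p < 0.05 arises in about 26 to 44% of analyses per cognitive score. That compares with about 21 to 25% without selection and about 5% for the overall F-test. Selection accounts for about 5 to 20 points.

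Two stronger readings are not supported. The between-group ANCOVA is a separate analysis and is unaffected, so nothing here bears on the treatment comparison. Nor can a firm rate be given for one disease within one arm: about 17 patients (52 / 3) would follow only from an equal three-way split, which the Protocol does not state.

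**What to change.** Prespecify the full model: list the motor scores that enter and any other covariates, and keep all of them. Test the motor scores together with one F-test per cognitive score. Interpret individual coefficients only if that test is significant, or adjust them for multiplicity. Reporting all coefficients with ordinary intervals and no such gate would not be enough, since about 21 to 25% of null analyses would still show one that excludes zero.

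Where the sample is too small for the full model, or if AIC selection is kept, report the selected model as descriptive, without p-values or confidence claims. For example, at n = 17 a model with six motor scores, age and baseline cognition leaves 17 − 9 = 8 residual degrees of freedom.

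The cost is a line or two of analysis text and wider intervals for individual collinear motor scores. Patients, visits and sample size do not change.
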